5.3.1 Definition of Primary Endpoints

The primary endpoint family is 1) the annualized rate of change in the API ADAD Composite Cognitive Test total score and 2) the annualized rate of change in the FCSRT Cueing Index.

The API ADAD Composite Cognitive Test total score is computed from the following 5 cognitive test scores:

- Consortium to Establish a Registry for AD (CERAD) Word List: Recall ([Rosen et al. 1984](#); [Morris et al. 1989](#); [Mohs et al. 1997](#))
- Multilingual Naming Test ([Gollan et al. 2012](#))
- Mini-Mental State Examination (MMSE) for orientation to time ([Folstein et al. 1975](#))
- CERAD Constructional Praxis (a measure of visuospatial ability; [Morris et al. 1989](#))
- Raven's Progressive Matrices (a measure of nonverbal fluid reasoning and visuospatial abilities) Set A ([Raven 1976](#))

Specifically, the ADAD-API Cognitive Composite Test total score is calculated as $[(\text{Multilingual Naming Test Score}/15) + (\text{MMSE Score}/5) + (\text{Raven's Progressive Matrices Score}/12) + (\text{CERAD Word List Recall Score}/10) + (\text{CERAD Constructional Praxis Score}/11)] \times 20$.

If at least one of the primary analyses is statistically significant, then the trial will be deemed positive. Type I error will be controlled using a graph-based procedure ([FDA 2017](#); see Section 3.1).

5.3.2 Estimands

Primary endpoint estimands are defined on the basis of the following attributes.

- Population: *PSEN1* E280A mutation carriers as defined by the inclusion/exclusion criteria specified in the protocol (mITT)
- Treatments: crenezumab versus placebo either by SC administration or by IV administration

- Variables: 1) annualized rate of change in the API ADAD Composite Cognitive Test total score and 2) annualized rate of change in the FCSRT Cueing Index
- Intercurrent events:
 - Events that lead to treatment withdrawal due to an adverse event. A treatment strategy will be applied where all observed values will be used regardless of the occurrence of the intercurrent event.
 - Death not due to AD. A hypothetical strategy will be applied where all values will be censored after the occurrence of the intercurrent event.
 - Death due to AD. All values on the primary endpoint after this event will be imputed as 0, the worst score possible
 - Pregnancy that leads to treatment withdrawal. A treatment strategy will be applied where all observed values will be used regardless of the occurrence of the intercurrent event.
 - Resumption of dosing after treatment discontinuation post-protocol amendment, version 8. A treatment policy strategy will be applied where all observed values will be used regardless of the occurrence of the intercurrent event.
 - Dose change from SC to IV administration. A treatment policy strategy will be applied where all observed values will be used regardless of the occurrence of the intercurrent event.
 - Events that lead to treatment interruption or withdrawal due to coronavirus disease 2019 (COVID-19) diagnosis. A hypothetical strategy will be applied where all primary efficacy data will be censored between COVID-19 diagnosis and recovery (if recovery date is missing, then all primary efficacy data after COVID-19 diagnosis date will be censored).
 - *Concurrent use of protocol-defined prohibited medications that can potentially impact cognition (e.g., anti-psychotics, anticonvulsants, benzodiazepines, etc.). A treatment policy strategy will be applied where all observed values will be used regardless of the occurrence of the intercurrent event.*
- Population-level summary: difference in annualized rate of change between the mutation carrier crenezumab arm and mutation carrier placebo arm

5.3.3 Main Analytical Approach for Primary Endpoint Family

The primary analysis on both primary endpoints will be performed using a RCRM (Richeldi et al. 2014; Flaherty et al. 2019; Hu et al. 2021) with a missing at random (MAR) assumption. This model will include all observations, including baseline scores as the response variable. The RCRM will include the randomization stratification factors described in Section 5.3 as fixed effects with an intercept, and will include the categorical treatment groups as interaction terms with time; *stratification factor(s) may be removed from the model if there is risk of non-convergence or sparse strata (in case*

of non-convergence, stratification factors will be removed in the order of the smallest number of observations in any cell caused by that stratification factor).

Participant-level random intercept and random slope are also included in the model, where an unstructured covariance between the random intercept and random slope is assumed. The RCRM is constructed as follows:

$$Y_{ij} = \alpha + (\text{Randomization Factors})_i + u_{0i} + (\beta + \beta_x l_{x,i} + u_{1i}) t_{ij} + \varepsilon_{ij}$$

where Y_{ij} is the score for participant i at visit j ; t_{ij} is the duration in the unit of year after first drug intake for participant i at visit j ; $l_{x,i} = 1$ if participant i in a *PSEN1* E280A mutation carrier is in the crenezumab mITT group, and $l_{x,i} = 0$ if participant i is a *PSEN1* E280A mutation carrier is in the placebo mITT group; u_{0i} and u_{1i} are random intercept and random slope, respectively, for the i^{th} participant; ε_{ij} is the random error for the i^{th} participant at visit j . The crenezumab treatment effect on the rate of change is quantified by β_x ; the 95% CI and p-value for crenezumab treatment effect will be presented. The crenezumab treatment effect compared with the placebo group on the relative reduction (RR) scale is calculated as $-\beta_x/\beta \times 100\%$; its estimate will also be presented; its 95% CI using bootstrap approach will also be provided.

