3.2.2 Rationale for Crenezumab Dosage

In this Phase II study, crenezumab 720 mg SC Q2W was selected as the dose and dosing regimen, following the results of the Phase II studies in sporadic AD; this dose provides similar exposures as the 15 mg/kg IV Q4W dose in Phase II that suggested a trend for efficacy in sporadic AD dementia. This SC dose has been administered in this study since August 2015 and has so far been well-tolerated. Since July 2019, a higher dose of 60 mg/kg IV Q4W is being offered to study participants as this is assumed to have a higher potential for efficacy and was also being investigated in Phase III studies in sporadic AD.

The Phase III studies (BN29552 [CREAD] and BN29553 [CREAD 2]) in patients with prodromal or mild (sporadic) AD tested a 4-fold higher dose (i.e., 60 mg/kg IV Q4W) of crenezumab than in Phase II compared with placebo. Based on results from a preplanned interim analysis of Study BN29552 assessing the safety and efficacy of crenezumab indicating that Study BN29552 was unlikely to meet its primary endpoint of change from baseline in CDR-SOB score, both Phase III studies were discontinued.

Study GN28352 continues given that this at-risk ADAD population differs from the sporadic prodromal to mild AD population in the following ways: the population is much younger, clinically asymptomatic at study entry, and carries a mutation that is specifically linked to amyloid metabolism. Approximately half of the carrier participants have been reported to have negative amyloid PET scans at baseline (Reiman et al. 2018). In addition, this *PSEN1 E280A* mutation is reported to be associated with an increased rate of amyloid accumulation in brain, as measured by amyloid PET compared with sporadic AD (Fleisher et al. 2015), suggesting the potential for crenezumab in delaying the progression of amyloid pathology may provide greater benefit in this patient population compared with sporadic AD. Furthermore, a quantitative systems pharmacology model of AD has been developed by Genentech and calibrated to both the ADAD (*PSEN1 E280A* mutation) and sporadic AD populations. Simulations from this model predict that both the 720 mg SC Q2W and 60 mg/kg IV crenezumab Q4W dosing regimens will delay the progression of amyloid

accumulation in the brain in the ADAD population, as measured by amyloid PET standard uptake ratio, with a greater effect associated with the 60 mg/kg IV Q4W regimen (internal data).

[figure not shown]

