3.2.3 Rationale for Participant Population

The study will enroll up to 200 *PSEN1 E280A* autosomal-dominant mutation carriers who meet research criteria for preclinical AD (Sperling et al. 2011b) and up to 100 kindred mutation non-carriers in Colombia. Participants will be enrolled at the University of Antioquia in Medellin, Colombia. As mentioned previously, people with ADAD mutations offer a scientifically compelling group for assessing the efficacy of putative prevention strategies in smaller and shorter trials because progression to MCI and dementia is certain. The well-characterized, world's largest *PSEN1 E280A* autosomal-dominant EOAD kindred in Colombia (Acosta-Baena et al. 2011) provides a rare opportunity to conduct a well-powered study.

The participant population will be selected to include mutation carriers in a stage of "preclinical AD," that is, they do not yet meet criteria for MCI or dementia (Reiman et al. 2010; Sperling et al. 2011b) but are destined to develop AD dementia by virtue of their ADAD mutation status.

In order to maximize the chances of observing a change in clinical and biomarker outcomes during the ≥ 5 -year treatment period of this trial, the enrolled participant population will be 30 years of age or older. The preclinical population ≥ 30 years of age was the population in which the empirically derived API ADAD Composite Cognitive Test Battery was developed and determined to be sensitive in tracking decline. Furthermore, imaging data in Colombian *PSEN1 E280* mutation carriers suggests that amyloid accumulation begins around the age of 30 (Fleisher et al. 2012). Therefore, this preclinical population may be optimal for detecting cognitive changes, the emergence of symptoms indicative of MCI due to AD, and amyloid-related biomarker changes.

A non-carrier group from the same kindred in Colombia will also be enrolled. The primary rationale for including non-carriers is to maintain blinding to genotype status to study participants, blinded study site personnel, and the Sponsor. The community standard in Colombia is to not be apprised of one's mutation carriage status in either research or clinical contexts. The inclusion of mutation non-carriers will also provide a genetic kindred control against which to explore the rate of clinical progression and biomarker changes in ADAD mutation carriers. The mutation non-carriers will be dosed only with placebo.

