3.8 MINIMIZATION OF BIAS

The trial is a Phase II, single-center, randomized, double-blinded, placebo-controlled study of the effects of crenezumab on clinical outcomes and biomarkers, in ADAD mutation carriers, with a non-randomized study of the effects of placebo in carriers and non-carriers.

In Study Period A, eligible carrier participants for the randomized clinical trial will be randomized in a 1:1 ratio (active to placebo) using an interactive voice or Web-based response system (IxRS) to prevent bias in treatment assignment.

Randomization among carriers will be stratified by age, education, *APOE* ϵ 4 carrier status (carrier vs. non-carrier), and baseline CDR zero versus CDR non-zero in order to maximize treatment group comparability. In Study Period B, all carrier participants will receive crenezumab and non-carrier participants will receive placebo.

Participants, study site personnel who will evaluate participant status, contract research organization (CRO) personnel who will review participant eCRFs, other Sponsor agents (with the exception of the IxRS provider), and Sponsor personnel involved in study conduct will be blinded to treatment assignments *at least* through the end of Study Period A. Because of the physical characteristics of the study drug, investigators and study drug administrators should implement strategies to maintain the blind, which are outlined in the pharmacy manual. Pharmacists and drug administrators will be unblinded to study drug allocation due to slight variations in color of active drug and placebo. Pharmacists and study drug administrators will not participate in any portion of the study outside requirements of drug preparation and administration. For further details, please refer to the pharmacy manual.

The investigator will be unblinded to study drug allocation only if the identity of the study drug is essential for participant management in the case of an serious adverse event. The investigator will contact the Sponsor, or medical designee, to discuss the medical details and options for unblinding. The iDMC will be unblinded to treatment assignment (see Section 3.10).

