3.10 ADMINISTRATIVE STRUCTURE

The study is sponsored by F. Hoffmann-La Roche Ltd (hereafter referred to as Roche). A joint leadership team comprised of the Banner Alzheimer's Institute and Roche will be responsible for governance, operating in partnership with the Neurosciences Group of the University of Antioquia. Crenezumab was in-licensed from AC Immune and is being developed by Roche. This trial will be managed by a primary CRO. A total of up to 300 participants will be enrolled in Colombia.

The randomization of participants will be managed by a central IxRS vendor using dynamic hierarchical randomization.

All laboratory tests of blood specimens will be performed by central laboratories or Roche, as appropriate.

A central imaging reader will determine the presence of cerebral VE and sulcal effusion by FLAIR MRI, and the presence of superficial siderosis of the CNS and cerebral micro- or macrohemorrhages by T2*-weighted GRE MRI scans.

An iDMC formerly referred to as the DSMB will be utilized during the conduct of this trial to periodically review unblinded safety and efficacy data *during Study Period A*.

In addition to periodic review of safety and efficacy data, the iDMC may make recommendations regarding study conduct. Details of the iDMC membership and roles are detailed in the iDMC Charter. *During Study Period B, an internal monitoring committee comprised of Sponsor employees not affiliated with the conduct of the trial will monitor safety.*

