3. SAMPLE SIZE DETERMINATION

This study will enroll up to 300 participants: up to 200 participants will be enrolled in the carrier cohort and up to 100 participants will be enrolled in the non-carrier cohort. Participants in the carrier cohort will be randomized in a 1:1 randomization ratio to active treatment or placebo. The study was initially powered to compare the mean change from baseline over 260 weeks in the API ADAD Composite Cognitive Test total score between the active treatment group and the placebo group. Assuming a 25% dropout rate with use of two-sided testing at the overall 0.05 level, a placebo group coefficient of variation of 65% for the Week 260 change scores ($= 100\% \times$ standard deviation of

[figure not shown]
placebo participant change scores/mean of placebo participant change scores) and 100 participants per arm, the study will have at least 80% power to detect a true effect of 30% reduction of the mean decline in the API ADAD Composite Cognitive Test total score in the placebo group using a t-test. Participants in the non-carrier cohort will all receive placebo and will be included in the study in order to maintain the genotype blind.

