5.4 SECONDARY ENDPOINTS ANALYSES

The continuous secondary efficacy endpoints will be analyzed using the same primary statistical model as for the primary endpoints. All time-to-event endpoints will be analyzed with a stratified log-rank test using the primary analysis stratification factors. Within each time-to-event endpoint, the hazard ratio (HR) for recurrence will be estimated using a stratified Cox proportional hazards model, and the 95% CI for the HR will be provided. Stratification factor(s) may be removed from the stratified analyses if there is risk of non-convergence or sparse strata (*in the case of non-convergence, stratification factors will be removed in the order of the smallest number of observations in any cell caused by that stratification factor*).

5.4.1 **Key/Confirmatory Secondary Endpoints**

The key secondary endpoints are:

- *Annualized rate of change in mean cerebral fibrillar amyloid accumulation using florbetapir PET from a predefined ROI*
 - *SUVrs will be derived from florbetapir PET images using a composite region of interest (including frontal, temporal, parietal, and cingulate cortices) with a subcortical white matter reference region*
- Time to progression from preclinical AD to MCI due to AD or from preclinical AD to dementia due to AD
- Annualized rate of change in the CDR Scale-Sum of Boxes
- Time to progression to non-zero in CDR global score
- Annualized rate of change in a measure of overall neurocognitive functioning: RBANS total score

Time to progression is calculated from the time at baseline, which is the last record on or prior to the first baseline reference date; the baseline reference date is either the first exposure date or the randomization date if the first exposure date is missing.

A gatekeeping strategy will be used for testing hypotheses of the key secondary outcomes using the graph-based type I error approach described in Section 3.1, the key secondary outcomes will be tested only if both the primary endpoints are statistically significant. All the tests will be done based on a two-sided $\alpha=0.05$. The tests in the key secondary outcomes will be done in sequential order specified in the following:

1. Annualized rate of change in mean fibrillar amyloid accumulation in a composite region (including frontal, temporal, parietal, and cingulate cortices) with a subcortical white matter reference region using florbetapir PET

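### The primary model adjusts the starting score for the randomisation factors but not the slope, which is the endpoint; if the factors predict decline, precision is given up

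*SAP*

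**What the plan says.** Both primary endpoints are annualised rates of change, tested at alpha 0.04 (API ADAD composite) and 0.01 (FCSRT Cueing Index). The SAP tests them in a random coefficient regression model (RCRM), of which Section 5.3.3 says: "The RCRM will include the randomization stratification factors described in Section 5.3 as fixed effects with an intercept". Treatment group is the only term given an interaction with time. The equation agrees:

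Y_ij = alpha + (Randomization Factors)_i + u_0i + (beta + beta_x I_i + u_1i) t_ij + e_ij

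The treatment effect is beta_x. A derived summary also rests on the slope terms: "The crenezumab treatment effect compared with the placebo group on the relative reduction (RR) scale is calculated as" −beta_x/beta × 100%.

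The model reaches beyond the primaries. SAP 5.4 adds: "The continuous secondary efficacy endpoints will be analyzed using the same primary statistical model as for the primary endpoints".

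SAP 5.3 says the analysis is adjusted for age, education, APOE4 status and baseline CDR (zero or non-zero). Protocol 4.10.3.1 describes a test on annualised rate that adjusts for selected baseline characteristics and randomisation factors.

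**The concern.** A factor on the intercept shifts where a participant starts. It does not let participants in different strata decline at different rates. If a factor predicts decline, that variation stays in the random slope u_1i and enters the standard error of beta_x.

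Allocation makes this more wasteful. Protocol 3.8 says: "Randomization among carriers will be stratified by age, education", APOE4 status and baseline CDR; Protocol 3.10 says it is done "using dynamic hierarchical randomization". Balance on the factors removes their contribution from the treatment contrast, yet the model still counts it as noise. The standard error is then too large and the test conservative.

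The documents make differing slopes plausible without quantifying them. Protocol 3.2.3 sets the age floor of 30 "In order to maximize the chances of observing a change in clinical and biomarker outcomes", and Protocol 3.2.2 reports: "Approximately half of the carrier participants have been reported to have negative amyloid PET scans at baseline". Carriers aged 30 to 60, some with non-zero CDR, span several disease stages.

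At stake is the precision of both primary tests and of the continuous secondaries. Protocol 3.2 reports that only 252 of 300 planned participants could be recruited from this kindred, so more carriers cannot be enrolled to make it up.

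**Working it through.** **1. The plan's own figure.** SAP 3 assumes "a placebo group coefficient of variation of 65% for the Week 260 change scores", a 30% reduction, 25% dropout, 100 per arm and a two-sided 0.05 t-test.

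- Completers per arm: 100 × 0.75 = 75.
- Standardised effect: 0.30/0.65 = 0.4615.
- Noncentrality: 0.4615 × √(75/2) = 2.826.
- Power: 80.2% (noncentral t) or 80.7% (normal).

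The stated 80% reproduces. It uses no covariates, so this point does not affect it.

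**2. Rough size by formula.** If the factors explain a share R2 of the variance, full adjustment replaces SD by SD × √(1 − R2). With 75 per arm:

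| R2 | alpha 0.04 | alpha 0.01 |
|---|---|---|
| 0% | 78.0 | 59.9 |
| 5% | 80.1 | 62.7 |
| 10% | 82.3 | 65.7 |
| 20% | 86.6 | 72.0 |
| 30% | 90.7 | 78.9 |

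This overstates the gain for the RCRM, because only the slope part of the variance is reduced, and because under balanced allocation the unadjusted estimate already benefits. Hence the simulation.

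**3. Simulation of the printed model.** REML, 6,000 replicates per scenario.

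- From the documents: 84 per arm (SAP Appendix 2), composite visits to Week 416, CV 65%, 30% reduction, 25% stopping early.
- Assumed: follow-up uniform over 260 to 416 weeks; slope making up 70% of the variance of Week 260 change; four binary factors with prevalences 50/50/25/15% and unequal shares of the explained slope variance; minimisation with a 0.8 biased coin; R2 itself.
- Scale: placebo slope −1 per year, SD of 5-year change 0.65 × 5 = 3.25.

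Power (%), printed model → centred factor-by-time:

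| R2 | alpha 0.04 | alpha 0.01 |
|---|---|---|
| 0% | 87.7 → 87.3 | 73.7 → 73.1 |
| 5% | 87.5 → 88.4 | 72.9 → 74.5 |
| 10% | 88.0 → 89.8 | 73.4 → 76.9 |
| 20% | 89.6 → 92.8 | 74.7 → 82.2 |
| 30% | 90.5 → 95.3 | 76.7 → 88.1 |

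The levels are not the trial's own power; the differences are what matter. Monte Carlo error on each figure is about 0.4 to 0.6 points.

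- **Standard error at R2 20%.** Printed model 0.0928 against a true SD of 0.0867, ratio 1.07. Adjusted model 0.0846 against 0.0855.
- **Information at R2 20%.** (0.0928/0.0846)² = 1.203, and 168 × 0.203 ≈ 34 extra carriers. The figure at R2 10% is about 15.
- **Null rejection of the printed model at nominal 0.04.** 0.032, 0.026 and 0.022 at R2 10, 20 and 30%.
- **Smaller effect.** For a 25% reduction at alpha 0.04, power goes from 73 to 76 (R2 10%) and from 75 to 81 (R2 20%).

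**4. Robustness.**

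- *Simple randomisation, R2 20%.* The printed model is calibrated (null 0.044), but power still goes 88.3 → 92.4 / 74.6 → 81.7.
- *Slope share 50 to 90%, R2 20%.* The gain is 2 to 4 points at 0.04 and 5 to 10 at 0.01.
- *A simpler simulation:* 76 per arm, 12 complete visits over 5 years, one factor, alpha 0.05, balanced allocation. Power 85.7 → 87.9, 88.7 → 92.5 and 89.5 → 94.5 at R2 10, 20 and 30%. With intercept–slope correlation 0.3, 90.6 → 94.0 at R2 20%.
- *A third, by GLS:* 84 per arm, visits to Week 416, minimised allocation. At R2 20%, 91.3 → 93.6 / 79.1 → 85.5, printed SE 0.0909 against a true SD of 0.0847. The gain persists with intercept–slope correlation 0.4.

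**5. Other planned analyses.** The MMRM (SAP 5.3.4) has factor main effects on change from baseline but no factor-by-visit terms. The robust-variance RCRM keeps the same fixed effects. Neither alters the primary test.

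**The case against.** The strongest reply is that nothing is wrong: the printed model estimates the stated estimand without bias, controls type I error and meets its planning target. That stands, and it fixes the nature of the point as a forgone gain. The printed model's simulated power does not fall as R2 rises; it goes from 87.7 to 90.5 at alpha 0.04.

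Second, R2 is assumed. Amyloid status is not a randomisation factor, and the age floor says nothing directly about slopes within ages 30 to 60. That stands too. The passages show a population mixed in disease stage, not that these four factors predict decline. At R2 5% or less the effect at alpha 0.04 is between −0.4 and +0.9 points.

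Third, the alpha 0.01 column borrows the composite's CV for the FCSRT, and 0.01 is only that endpoint's starting level; it can be tested at 0.05 if the composite succeeds. The trial is positive if either primary succeeds. Combining the simulated powers with an assumed correlation of 0.3 to 0.7 between the test statistics, the gain in winning at least one is about 0.5 to 0.8 points at R2 5%, 1.2 to 1.6 at 10%, and 2 to 3 at 20%. This is a fair limit on the benefit.

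Fourth, the common-close design was adopted to hold 80% power despite the recruitment shortfall. True, but it does not conflict with using the same data more precisely.

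Fifth, more terms raise the risk of non-convergence. The SAP already has a removal order that can be extended.

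**Conclusion.** The point holds as an efficiency recommendation. The intercept-only placement is explicit in both the text and the equation of SAP 5.3.3, and it falls short of the protocol's stated aim of a rate comparison adjusted for these factors. Simulated power gains are about 2 points at alpha 0.04 and 3.5 at alpha 0.01 if the factors explain 10% of slope variance, and about 3 and 7.5 points at 20%.

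These sizes rest on an assumed R2, on the composite's CV applied to both endpoints, and on an assumed allocation algorithm. The conservatism of the printed test depends on balanced allocation; the power gain does not. Confidence is high on the structure and medium on the size. The trade is lopsided: about half a point is lost if the factors are uninformative, and several points may be gained if they are not.

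**What to change.** Before unblinding, add randomisation-factor × t_ij terms to the RCRM for both primaries and for the continuous secondaries that use it. Keep beta_x as the tested parameter.

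Centre each factor at its mean in the mITT carriers, so that beta remains the average placebo slope. This matters for the relative reduction: uncentred, in the R2 20% simulation beta becomes −0.65 instead of −1.00, and a true 30% reduction would print as 0.30/0.65 = 46%.

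For non-convergence or sparse strata, drop a factor's time interaction first and then its main effect, in the SAP's existing order.

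Carry the centred terms into the instantaneous-loss, SC/IV, quadratic, control-based imputation and delayed-start models. In the single-arm fits of the control-based imputation, centre at the pooled mITT carrier means, not at arm means.

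The cost is a small edit across several model statements and about four extra parameters for about 168 carriers, if each factor has two levels as in the SAP 5.3.5.1 subgroup list.
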